4. TRIAL AND DRUG SAFETY

4.1 Risks of FGR to the Fetus

Early-onset FGR carries significant fetal risks of premature birth. Following diagnosis, those babies requiring delivery <32 weeks gestation carry approximately an 8% risk of stillbirth or neonatal death, with those born <28 weeks gestation having a significantly higher perinatal mortality rate ^{40,41}. Around 30% of survivors will suffer serious neonatal morbidity ⁴⁰. Furthermore, 8% are found to have neurodevelopmental impairment at two years of life ⁴². These numbers are likely to be an underrepresentation as they are from a trial population, which was closely surveyed compared to the general population.

4.2 Risks of FGR to the Mother

With approximately 97% of FGR infants born <32 weeks delivered by caesarean section, the mother of a preterm FGR fetus faces the risks associated with morbidity and mortality relating to caesarean birth ⁴⁰. Furthermore, they also face a significant risk of morbidity and mortality from pre-eclampsia, which develops among 15 - 40% of women who have a growth-restricted fetus ^{43,44}.

4.3 Potential Risks of Melatonin Treatment

The most common side effects of melatonin are headache, dizziness, nausea and sleepiness ⁴⁵. Melatonin does not have any acute pharmacological effects on the nervous or vascular systems, apart from its benign but active impact on sleep mechanisms ⁴⁶. Extremely high doses of up to 800mg/kg of melatonin were safely administered to animals without deaths, meaning a median lethal dose could not be established. In humans, long-term treatment with high, daily doses of up to 10g melatonin did not cause any toxicity except for isolated cases of cutaneous flushing, abdominal cramps, diarrhoea, scotoma lucidum and migraine ⁴⁷.

Prolonged ingestion of 1g melatonin per day caused only subjective drowsiness but did not provoke any toxicity in the eyes, liver, kidneys and bone marrow ⁴⁸. In a phase II clinical trial conducted in the Netherlands, 1400 women were given 75mg melatonin nightly over 4-years, with no side effects reported ⁴⁹.

The safety of melatonin use in pregnancy was explored in early pregnant Sprague-Dawley rats, at doses ranging from 1 to 200mg/kg/day and did not affect antenatal mortality, fetal body weight or other measures of fetal wellbeing ⁵⁰. Maternal adverse effects seen at high doses, included mild sedation, reduced maternal weight gain and reduced food intake. This study sought to determine the maternal and fetal no adverse effect level (NOAEL). The NOAEL is the exposure level where a particular substance does not statistically or biologically significantly increase the frequency or severity of adverse effects in an exposed population compared to a suitable control population. The maternal NOAEL in this study was found to be 100mg/kg/day, the fetal NOAEL was established at $\geq 200\text{mg/kg/day}$ when administered to the mother. The maternal lowest observed adverse effect level toxicity was 200mg/kg/day. With the above information taken in context, the Australian Therapeutic Goods Administration (TGA) has assigned melatonin a Pregnancy Category B3 classification.

We have recently completed a phase 1 trial (NCT01695070) using melatonin supplementation in pregnancy, as well as a clinical trial in women with pre-eclampsia (ACTRN12613000476730) using the same dose as proposed for this trial, and to date no adverse effects have been identified in the mother, fetus or neonate ^{13,38,51,39}.

5. TRIAL DESIGN

PROTECT Me aims to be a multicentre, triple-blinded, randomized, parallel group, placebo controlled trial.

6. TRIAL POPULATION

Pregnant women with a singleton pregnancy complicated by severe fetal growth restriction identified at 23+0 – 31+6 weeks' gestation will be approached for recruitment.

6.1 - Inclusion Criteria

1. Singleton Pregnancy
2. Severe fetal growth restriction, defined as:
 - Abdominal circumference \leq 3rd centile for gestational age according to charts supplied that have been adapted from Westerway et al ⁵²; or
 - Abdominal circumference $<$ 10th centile ⁵² in combination with at least one abnormal fetoplacental Doppler study, being:
 - Uterine artery (raised pulsatility index \geq 95th centile)⁵³
 - Umbilical artery (pulsatility index \geq 95th centile⁵⁴ or absent/reversed end-diastolic flow)
3. Confirmed 23+0 – 31+6 weeks' gestation
4. Age \geq 18 years
5. Understand English

6.2 - Exclusion Criteria

1. A fetus with a known chromosomal, major structural anomaly or non-placental cause of fetal growth restriction
2. Pregnancies requiring immediate delivery (e.g. absent A wave in ductus venosus, preterminal CTG or biophysical profile)
3. Co-recruitment in another clinical trial where a pharmaceutical product or nutritional supplement impacting on oxidative stress is the trial intervention.
4. Currently prescribed Fluvoxamine

6.3 - Withdrawal of Trial Participants

All participants are free to withdraw from the trial at any point if they wish. The study power calculation allows for a 5% drop-out rate. This drop-out rate is a conservative estimate of what has been observed in other clinical trials performed within our institution. Ongoing clinical care will continue as determined by the treating clinical team following best practice

guidelines. Data collected to the point of withdrawal will be retained unless the participant specifically advises against this.

Pregnancy, birth and postnatal outcome data will be collected from the participant's hard copy clinical notes, relevant Hospital databases and directly from the participant. Data related to the baby/child will similarly be collected from hard copy clinical notes and relevant Hospital databases. If the participant chooses to discontinue the trial intervention, participation in sample collection at birth and the neonatal outcome follow-up will still be offered.

7. SAMPLE SIZE AND POWER CALCULATIONS

The required sample size has been calculated to detect if melatonin supplementation affords a clinically relevant difference in neurodevelopmental outcomes among survivors. An increase of 4-5 quotient points in the Bayley-4 Cognitive scale has been deemed sufficiently clinically meaningful to drive changes in health policy previously ⁵⁵. Power analysis shows that 69 participants per group will allow the detection of a difference in the Bayley-4 cognitive score of 5 points between the two groups, with a power of 90% and an alpha level of 0.05, using 2sided T test for comparison. This assumes a standard deviation of 9 ⁶ and that, on average, the growth restricted infant has been shown to have a cognitive score 5 points lower than the healthy preterm infant and 8 points lower than the healthy term infant⁶. Typically, the Bayley-4 score has a standard deviation of 15, however reduced variability has been seen in the FGR population and this has informed the standard deviation used here. Among pregnancies complicated by early onset FGR a perinatal loss rate of ~15% is commonly observed ^{41,56}. Allowing for a perinatal loss rate of 15%, an extra 42 women will be recruited. Assuming an additional 5% loss to follow-up rate, we will aim to recruit an extra 14 participants.

This trial also aims to assess whether the impact of melatonin is different at different gestational ages. Therefore, a sub-analysis will be undertaken to compare those with early onset FGR identified <28 weeks' gestation to those with late-onset FGR identified between 28-31+6 weeks gestation. To ensure that this sub-analysis is adequately powered, participants recruited will be randomized to either melatonin or placebo based on their gestational age at diagnosis. Therefore, recruiting 83 participants per group will see the overall trial aiming to recruit 332 participants (see figure 1).

[figure not shown]

Figure 1: Flowchart of Participant Assignment to Trial Arms.

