9. RANDOMISATION

Randomisation will be via an on-line computerised randomisation service. Randomisation will occur on a 1:1 ratio of melatonin to placebo with the goal of 83 participants randomized to each of the two trial arms stratified by gestational age at recruitment and the presence or absence of abnormal Dopplers. At the time of recruitment, each participant will be assigned a unique trial code. Subsequently, all data and tissue samples collected from the participant will be stored only with this associated code. Thus, all data and tissue samples are deidentified at the point of collection, but with the capability to re-identify them in the future for data verification, research audit or safety (e.g. needle-stick injury).

Furthermore, it will be possible to break the randomization code and reveal treatment group if necessary, such as in the event of a potential treatment-related serious adverse event occurring.

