 - Compromise of confidentiality of data, such as protocol violations, unblinding etc.
 - Scientific or therapeutic advances that may impact on participant safety or the ethics of the study

We would advise the DSMC to advocate complete cessation, or re-evaluation, of the trial conduct, if it is evident that either arm of the trial is associated with a statistically significant increase in or a 50% increased rate above the baseline ratio of any adverse events.

16.7.3 - Information presented to the DSMC

All data will be presented to the DSMC without any participant personal identifiers associated with it. The interim analysis results will not be available to anyone external to the DSMC unless the trial is required to cease prematurely.

16.7.4 - Frequency of DSMC reporting

We will provide information to the DSMB following the recruitment of 100 participants and again following recruitment of 200 participants. Information will be provided at other times if requested by the DSMC or the Sponsor, Monash Health Research Directorate and Human Research Ethics Committee. No interim statistical analyses of the primary or secondary outcomes are planned.

16.7.5 - Notification to the Monash Health Research Directorate and HREC of DSMC findings

The Lead PI will notify the sponsor, Monash Health Research Directorate and the Human Research Ethics Committee, of the DSMC's findings at each of the safety assessment time points.

The Lead PI will notify the DSMC of all SAE/AEs submitted to the sponsor, Monash Health.

16.8 - Reporting to Research Support Services

Forms will be emailed to Research Support Services at:
[contact]

AE correspondence will be included in the next HREC agenda. Within a week of the meeting, acknowledgement will be forwarded to the Lead Principal Investigator and Study Coordinator. In order to respond to researchers in a timely manner, the Research Support Services will not send a formal letter. Instead, the cover letter/report form submitted by the researcher will be signed and dated by the HREC Chair or designee. A copy of the stamped letter will be scanned to the Lead Principal Investigator and Study Coordinator as verification.

16.9 - Events that will not be reported

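### Loss allowance in Section 7 is added to the required number rather than divided out, so 332 recruited gives about 268 assessed children, not 276; Section 9's 83 per trial arm (166) disagrees with 332

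*Protocol*

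**What the plan says.** Section 7 of the protocol starts from the number of children needed at the end: "Power analysis shows that 69 participants per group will allow the detection of a difference in the Bayley-4 cognitive score of 5 points", "with a power of 90% and an alpha level of 0.05, using 2sided T test for comparison", with an assumed SD of 9. It then adds two allowances: "Allowing for a perinatal loss rate of 15%, an extra 42 women will be recruited", and "Assuming an additional 5% loss to follow-up rate, we will aim to recruit an extra 14 participants". Because the trial is also meant to be adequately powered for a sub-analysis by gestational age (below 28 weeks, and 28 to 31+6 weeks), there are four arm-by-stratum cells, and the section concludes that "recruiting 83 participants per group will see the overall trial aiming to recruit 332 participants".

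Section 9 gives the randomisation target as 1:1 allocation "with the goal of 83 participants randomized to each of the two trial arms", stratified by gestational age and Doppler status. Section 10.1 confirms that the arms are two: melatonin and placebo. Section 16.7.4 schedules information for the safety committee "following the recruitment of 100 participants and again following recruitment of 200 participants".

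**The concern.** There are two separate points.

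**The loss allowance.** Perinatal loss and loss to follow-up act on the women who are recruited. To finish with a required number, one divides that number by the fraction expected to remain. Section 7 instead takes the percentages of the required number and adds them, which always falls short. The section claims 90% power with 69 per group, and the recruited number does not quite deliver that.

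**The randomisation target.** Two arms of 83 make 166, not 332. The randomisation section is where a reader looks for the number to be allocated, and it should agree with the sample-size section. If 166 were taken as the total, the sub-analysis that Section 7 sets out to power would have about half the children it needs.

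**Working it through.** **Inputs.** From Section 7: difference 5 points, SD 9, two-sided alpha 0.05, power 90%, 69 per group, perinatal loss 15%, loss to follow-up 5%, 83 per group, 332 overall. From Section 9: 83 in each of two arms. From Section 16.7.4: reports after 100 and 200 recruited. Power figures below use the noncentral t distribution.

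**1. Reproduce the 69.** n = 2(1.960 + 1.282)² × 9²/5² = 68.1, rounded up to 69 per group. The t-test solution is 69.06, and power at 69 is 89.97%. The printed 69 holds.

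**2. Reproduce the 332.**
- Four cells: 4 × 69 = 276. This is not printed, but 332 − 42 − 14 = 276 returns it.
- 0.15 × 276 = 41.4, rounded up to 42.
- 0.05 × 276 = 13.8, rounded up to 14.
- 276 + 42 + 14 = 332, and 332/4 = 83.

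All printed figures follow from the additive route. Dividing by the retained fraction does not give 332:
- losses in sequence: 276/(0.85 × 0.95) = 341.8, so 342; rounding up within cells, 69/0.8075 = 85.4, so 86 per cell and 344 in all;
- both losses as shares of those recruited: 276/0.80 = 345; within cells, 69/0.80 = 86.25, so 87 per cell and 348 in all.

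**3. What 332 yields on the stated loss rates.**

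| | Sequential loss (0.85 × 0.95 = 0.8075) | Both from recruited (0.80) | Required |
|---|---|---|---|
| Assessed overall | 332 × 0.8075 = 268.1 | 332 × 0.80 = 265.6 | 276 |
| Per cell | 83 × 0.8075 = 67.0 | 83 × 0.80 = 66.4 | 69 |
| Within-stratum power, 5 points, SD 9 | 89.1% | 88.8% | 90.0% |

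Equivalently, 332 gives 276 only if combined loss is 1 − 276/332 = 16.9%; the stated rates combine to 1 − 0.8075 = 19.25%.

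**4. Pooled comparison.** 166 × 0.8075 = 134 assessed per arm, giving 99.5% power at SD 9.

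**5. Section 9 against Section 7.** 2 × 83 = 166; Section 7 has 332, which is 166 per arm. A report after 200 recruited cannot occur in a trial of 166, so 332 is the intended total and 83 must mean per arm within each gestational-age stratum. If 166 were the total, 166 × 0.8075 ≈ 134 would be assessed, 67 per arm (about 89% power overall). With equal strata, which is an assumption, that is about 33.5 per arm per stratum and about 61% power within a stratum.

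**The case against.** The strongest reply is that the loss allowance hardly matters. It concerns 8 of 276 children and 0.9 points of power, and the inputs are softer than that. Section 7 gives the 15% only as an approximate rate. With 5% loss to follow-up, 332 still yields 276 if perinatal loss is about 12.5% (332 × 0.875 × 0.95 = 276), and it yields 290 at the 8% that Section 4.1 quotes for deliveries before 32 weeks. Raising the SD from 9 to 9.2 lowers power at 69 per group to 88.7%, more than the whole arithmetic error. At 15, which Section 7 names as the usual SD, within-stratum power is 49% at 69 per group and 48% at 67.

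This stands as to size: the error is small. It does not make the derivation right, since the section states its own rates and its own power and the two do not match.

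On Section 9, the sentence goes on to mention stratification, so it can be read as a loose form of 83 per arm per gestational stratum. That is probably what was meant. But the sentence also names Doppler status as a stratification factor, so it does not lead to 332 as written. Figure 1 may show the cell numbers; it was not available to this review, and it would not alter the sentence.

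Two cautions apply to any corrected text. Section 4.1 says perinatal mortality is higher for births below 28 weeks, so the earlier stratum may end below 67 per arm. And 89% is the power of a treatment comparison inside one stratum. A test of whether the effect differs between strata by 5 points has only about 62% power at 67 per cell (standard error 9 × √(4/67) = 2.20, normal approximation).

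**Conclusion.** Both points hold. The loss allowance is calculated on the wrong base: 332 recruited is expected to give about 268 assessed children, 67 per cell, and 89.1% within-stratum power rather than 90.0% (266 children and 88.8% if both losses are shares of those recruited). The effect is small, confined to the within-stratum comparisons, and of no consequence for the pooled comparison. Section 9's goal reads as 166 against 332; this is a wording error, and the more useful of the two to correct.

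The figures assume SD 9, a 5-point difference, equal cells, and losses of 15% and 5% that are uniform across arms and strata.

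**What to change.** Keep 332 and change two sentences.

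- **Section 7**, after the total: *Recruiting 332 is expected to give about 268 assessed children (67 per arm per gestational-age stratum) and about 89% power within a stratum for 5 points at SD 9, assuming a uniform 15% perinatal loss and 5% loss to follow-up.* Leave it labelled as within-stratum power, so that it is not read as power for a comparison between strata.
- **Section 9**, in place of the present goal: *166 participants per arm, 83 per arm within each gestational-age stratum.*

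This needs no extra participants and no change to the design; the stated within-stratum power falls by about 1 point. Holding 90% under the stated loss rates would instead need 342 to 348 recruited, 10 to 16 more women, which the size of the shortfall does not call for.

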14. OUTCOME MEASURES

14.1 - Primary Outcome

Improved neurodevelopmental performance at 2 years of life among survivors of early onset FGR.

The ability of melatonin to protect the fetal brain in the setting of severe early-onset fetal growth restriction will be assessed by multiple assessments across the first 2 years of life. The trial is powered to detect a difference in neurodevelopmental performance at 24-36 months corrected age on the Bayley-4. Other tools of assessing brain development and neurocognitive performance will also include GMA and MRI at term, GMA again at 3-months corrected age and ITSEA at 24-36 months corrected age. These assessments will also be stratified depending on the fetal gestation and fetal Dopplers at the time of FGR diagnosis, with outcomes for those <28 weeks and between 28-31+6 weeks compared as a sub-analysis. Total mortality will be compared between melatonin and placebo.

14.2 - Secondary Outcomes

- Assessment of drug safety and tolerability: Maternal side effect profiles experienced, such as symptoms of drowsiness, abdominal cramps, flushing, migraines, gastrointestinal disturbance. This information will be collected from the participant medication diary.
- Maternal end-organ performance monitored through haematological and biochemical tests
- Fetal effects through assessing ultrasound parameters of fetal biometry (HC, BPD, AC and FL) and wellbeing (AFI, Doppler indices).

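### Section 7 claims adequate power to show that melatonin's effect differs by gestational age, but its only calculation sizes the treatment effect within each stratum

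*Protocol*

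**What the plan says.** Section 7 of the protocol opens with one power calculation: "Power analysis shows that 69 participants per group will allow the detection of a difference in the Bayley-4 cognitive score of 5 points", for a two-sided t-test with 90% power, alpha 0.05 and SD 9. It adds 42 women for a 15% perinatal loss rate and 14 for 5% loss to follow-up.

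It then sets a further aim: "This trial also aims to assess whether the impact of melatonin is different at different gestational ages". The sub-analysis is to compare FGR identified before 28 weeks with FGR identified at 28 to 31+6 weeks. On power it says: "To ensure that this sub-analysis is adequately powered, participants recruited will be randomized to either melatonin or placebo based on their gestational age at diagnosis". From this it concludes that "recruiting 83 participants per group will see the overall trial aiming to recruit 332 participants".

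Section 14.1 returns to the sub-analysis, "with outcomes for those <28 weeks and between 28-31+6 weeks compared as a sub-analysis", without saying that the treatment effect is the quantity compared. Section 7 gives neither a target size nor a power for a difference between the two strata's treatment effects.

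**The concern.** Whether the impact of melatonin differs by gestational age is a question of effect modification: the melatonin-placebo difference before 28 weeks minus the same difference at 28 to 31+6 weeks. The calculation in Section 7 answers another question, namely whether melatonin differs from placebo in a single two-group comparison. Repeating it in each stratum gives each stratum its own power but does not give that power to the contrast between them. Randomising by gestational age balances the arms within strata; it does not supply the power either.

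This matters because Section 7 offers the sub-analysis as the reason for the larger total. A reader told that it is adequately powered could take a null result as good evidence that the effects are alike. A reader could also take significance in one stratum and not the other as evidence that they differ.

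**Working it through.** **Inputs from Section 7:** difference 5 points, SD 9, two-sided alpha 0.05, power 90%, 69 per group, losses 15% and 5%, 83 per group, total 332.

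**Assumptions added here:** strata of equal size; 69 assessed per cell (the protocol's figure) or 67, from 332 × 0.85 × 0.95 / 4 = 67.0; differences in effects of 4 to 8 points, because the protocol gives no target.

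**1. Reproduce the plan's figures.** The t-test needs 69 per group (exact solution 69.06), and power at 69 is 90.0%. Four cells give 4 × 69 = 276. Then 15% of 276 = 41.4, rounded up to 42; 5% of 276 = 13.8, rounded up to 14; and 276 + 42 + 14 = 332 = 4 × 83. The figures reproduce, and they show that the same t-test was provided once per stratum.

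**2. Treatment effect within a stratum.** SE = 9 × √(2/n) = 1.532 (n = 69) or 1.555 (n = 67). Power for 5 points is 90.0% or 89.1%.

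**3. All-participant comparison.** With 138 or 134 per arm, power for 5 points is 99.6% or 99.5%.

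**4. Difference between the two stratum effects.** The variances add, so SE = 9 × √(4/n) = 2.167 (n = 69) or 2.199 (n = 67), with 4n − 4 degrees of freedom. Power from the noncentral t distribution:

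| Difference in effects (points) | n = 67 per cell | n = 69 per cell |
|---|---|---|
| 4 | 44.1% | 45.2% |
| 5 | 62.0% | 63.3% |
| 6 | 77.6% | 78.8% |
| 7 | 88.7% | 89.6% |
| 8 | 95.2% | 95.7% |

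Power of 80% is reached at 6.18 (n = 67) or 6.09 (n = 69) points, and 90% at 7.15 or 7.05.

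**5. Precision.** The 95% CI half-width for the difference in effects is 4.33 or 4.27 points. An estimate of zero would therefore leave 4 points inside the interval and 5 points outside it.

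**6. Separate tests as a substitute.** If the true effect were 5 points in both strata, the chance that exactly one stratum is significant is 2 × 0.90 × 0.10 = 18% (2 × 0.891 × 0.109 = 19% with 67 per cell).

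**7. Sensitivity.** For a 5-point difference in effects with 276 assessed, power is about 62% with a 40/60 split of the strata and 56% with 30/70. With SD 15, which Section 7 calls typical of the scale, it is 28% at 69 per cell.

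**The case against.** The strongest reply is that no sum in Section 7 is wrong. Read as separate comparisons within each stratum, set side by side, the sub-analysis has about 90% power in each, and that is evidently how 332 was built. This is true of the sizing. It does not meet the stated aim, which is whether the impact differs; step 6 shows how side-by-side significance can mislead.

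A second reply is that, with no target stated, the power claim is unsupported rather than shown to be false: a difference of 7 points or more would be detected with about 90% power. That is fair. But such a difference exceeds the whole 5-point treatment effect assumed. The benchmark in Section 7, "An increase of 4-5 quotient points in the Bayley-4 Cognitive scale has been deemed sufficiently clinically meaningful", applies to a treatment effect, so using 4 or 5 points for a difference between effects is an assumption. It is also right that a null estimate would exclude 5 points.

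Third, the four-cell structure is inferred from the arithmetic, and Section 9 speaks of 83 in each of the two trial arms. If that meant 166 in all, there would be about 34.5 assessed per cell and power for a 5-point difference in effects would be about 37%, so the point holds on either reading.

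Finally, the form of the comparison in Section 14.1 could be left to the SAP, and the question is not among the aims listed in Section 3. Both points limit the weight. Neither removes the power claim, which the protocol itself makes and which no SAP could make true for a 4- or 5-point difference at 332.

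**Conclusion.** The concern holds. With SD 9, equal strata and 67-69 assessed per cell, 332 gives 89-90% power for 5 points within each stratum and over 99% overall. For the difference in effects it gives only 62-63% at 5 points, and about 7 points are needed for 90%. SD 9 and equal strata are favourable assumptions; a larger SD or unequal strata would lower the power further. The defect is confined to the effect-modification claim and leaves the all-participant comparison untouched. It should be fixed.

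**What to change.** In Section 7, state what 332 provides under SD 9 and equal strata: about 89-90% power for 5 points within each stratum, over 99% for the all-participant comparison, and, for the difference in treatment effects between strata, 80% power at about 6 points and 90% at about 7. Remove the claim of adequate power for that last question, or label it exploratory. In Section 14.1, say that the treatment effect is compared between the strata, reported as a difference in effects with a 95% CI, and not judged by significance in each stratum.

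The cost is wording in two sections and a less favourable stated power for the sub-analysis. No more participants are needed. The alternative, sizing the trial for a 5-point difference in effects at 90% power, would need 137 assessed per cell (4 × 137 = 548), about twice the present 276, and is not proposed.
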